“Enhanced recovery after surgery,” or ERAS, is no longer a novel idea. However, its benefits are beginning to be seen beyond the early metrics of hospital stay and activities of daily living. Downstream benefits have included reduced complications, less readmissions (despite earlier discharges), less hospital resource consumption (cost), and improved postoperative quality of life. With the opioid epidemic increasingly discussed in both medical and lay literature, we are seeking to modify our enhanced recovery program in abdominal cancer surgery to reduce opioid exposure in the hospital. Medical literature has shown that oftentimes the first exposure or greatest exposure to opioids comes from an elective surgical event. Persistent opioid use (past 1yr) can be predicted by the size of a patient’s initial outpatient prescription **oral morphine equivalents (OME)**. And the **initial outpatient prescription OME can be predicted by the amount of opioids used in the last 24hrs of hospitalization**.

We recently analyzed 158 consecutive pancreatectomy patients’ opioid use by converting units into OME using an automatically generated download from our electronic health record. In our analysis, we found that intravenous patient-controlled anesthesia (IV-PCA) represented the largest contributor to total inpatient OME, even when universally paired with an ultrasound-guided regional anesthetic block with 72-hr liposomal bupivacaine. Median total OME (from all sources of pain control) for patients with IV-PCA was 525mg (range 28-4,362mg). Median OME contribution from IV-PCA alone was 373mg. **Only 5% of patients were discharged without opioids.** Median initial outpatient prescription OME was 316mg, far above the 200mg OME recommended by the CDC. We thus see an **opportunity to reduce opioid exposure** to increase the **proportion of opioid-free patients at discharge**. We are already embarking in improving our “usual care” enhanced surgical recovery bundle by using standardized non-narcotics and reducing initial IV-PCA settings.

HYPOTHESIS

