- We hypothesize that a **second, repeat QL block on postoperative day 4** will bridge the gap between the initial intraoperative QL block and ambulatory status, facilitating a rapid opioid wean and **thus increase the proportion of cancer survivors without postoperative outpatient opioid prescriptions**. Ultimately, this should reduce dissemination of opioids into the community and reduce the risk of persistent opioid use in survivors.

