- **Liposomal bupivacaine has become our standard of care for open surgery.** We use this in 90% of our pancreas patients, while the other 10% get epidurals. There is extensive experience using liposomal bupivacaine for regional blocks. This RCT does not focus on the use of the block per se (since it is routine care), but rather the timing of it.

Comparison Strategy:

The control arm patients will have usual care with just the single QL using ultrasound guidance placed in the OR. When the liposomal bupivacaine wears off, **there will be no second QL**. The **usual measures of non-narcotic bundle** [including acetaminophen, NSAIDs, muscle relaxers, and Lidocaine-secreting patches] and conversion from IV pain meds to oral pains will be done to reduce total opioid exposure and use. Due to risk of harm from injection of placebo, there will not be any sham procedure

Decision on Discharge Opioid Prescription

To avoid bias in one arm or the other, all discharge prescriptions will be standardized. Both arms will get standard non-narcotic bundles of acetaminophen 650mg q6hrs, celecoxib 100mg q12hrs, and methocarbamol 250-500mg q8hrs. Slight dose variations can be allowed here based on pharmacy availability (e.g. recent national shortage of methocarbamol 500mg pills). To standardize the opioids, we will use a multiplier of 5 days x the last-24hrs opioid pill count. This can be found easily in the electronic health record. We chose 5 days because the CDC recommends 7 days max prescription and less than 200mg OME. All patients have clinic appointments within one week of discharge and have phone numbers to call if their multimodal pain management plan is insufficient. The chance of this is very low considering these patients are on the same plan on discharge as they have been in the last 24hrs in the hospital. The multiplier of objective opioid pain pill use will be more useful than the subjective pain score which varies from patient to patient in their interpretation of that "smiley-face" Likert scale.

Interim Analyses:

One interim analysis will be performed when half of the patients (N=53) have been randomized and received treatment. The trial will be stopped due to futility if the p-value is >0.774 for the primary endpoint.

Anticipated Results:

Participant Flow Diagram: see Figure 1

Recruitment

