5.0 Statistics and Justification of Sample Size

For the primary analysis, we will perform Chi-squared test to compare the proportion of patients who are opioid-free on the discharge date between the two arms. As a secondary analysis, we will also perform the Cochran–Mantel–Haenszel test to take into account the stratification factors. In addition, stratified logistic regression analysis will be carried out to assess the difference between the two arms after adjusting for the stratification factors and other patient characteristics at baseline. Similar analyses will be performed for other binary secondary outcomes, such as discharge Rx dosage/size total OME <200mg (yes vs. no), opioids usage on postoperative days 30, 90, 180, and 365 (yes vs. no), etc. Two sample t-test or Wilcoxon rank-sum test will be used to compare continuous secondary outcomes such as total inpatient OME, cost, QOL scores, pain prescription dosage at first discharge, etc. Other statistical analyses may be performed as appropriate.

Based on historical data, we anticipate that 5% patients in the control arm will be opioid-free in their discharge prescriptions, while with the additional TAP block in the experimental arm, it will increase the proportion to 25%. Under this assumption, the study will require 106 **patients (53 per arm)** in order to have 84.5% power to detect such a 20% difference, using two-sided Chi-squared test and with 5% significance level. East6.3 was used for the sample size calculation. Assuming a liberal 10% dropout rate, a total of 118 patients will be enrolled from our single institution. Based

on our historical operation volume of 120 patients per year, we anticipate the ability to complete enrollment within 1 year of opening the protocol. One interim analysis will be performed when half of the patients (N=53) have been randomized and received treatment. The trial will be stopped due to futility if the p-value is >0.774 .

- Power and significance: 84.5% power ($\beta=0.155$) and $\alpha=0.05$ (two-sided)
- Baseline estimate of control group with no opioids on discharge day: **5%**
- Estimate of experimental: **25%**
- Sample size per arm: 53 pts
- Assume 10% dropout: 59 per arm
 - [1 year to complete enrollment]

In order to enroll the total 118 patients, we will screen up to 140 patients in order to account for screen failures and those who are ineligible due to aborted surgeries.

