9.0 Data Monitoring

This protocol will be monitored by the MD Anderson DSMB.

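### The futility cut of p > 0.774 has no direction: read with the plan's two-sided test, it stops near-ties but not results in which the second block trails control

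*Combined protocol and SAP*

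**What the plan says.** Section 4.0 (Interim Analyses) plans a single look: "One interim analysis will be performed when half of the patients (N=53) have been randomized and received treatment". The rule follows: "The trial will be stopped due to futility if the p-value is >0.774 for the primary endpoint". Section 5.0 repeats it without the reference to the endpoint: "The trial will be stopped due to futility if the p-value is >0.774". Neither place says whether the p-value is one- or two-sided, which direction counts, or whether a continuity correction is applied.

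The only primary test defined is the chi-squared comparison of opioid-free discharge. Section 5.0 sizes the trial "using two-sided Chi-squared test and with 5% significance level", with 53 per arm, "in order to have 84.5% power to detect such a 20% difference" (5% control, 25% experimental). The hypothesis in section 2.0 has one direction, that the second block will "thus increase the proportion of cancer survivors without postoperative outpatient opioid prescriptions".

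No other rule stops the trial on the primary endpoint. The review of the first 20 patients in section 4.0 concerns complications and pathway deviation. Section 9.0 says only "This protocol will be monitored by the MD Anderson DSMB".

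**The concern.** A chi-squared statistic has no sign. A large p-value means that the arms look alike; it does not say that the experimental arm is failing. For a hypothesised increase, a result with the experimental arm clearly behind is a stronger reason to stop than a tie. As written, the rule does the opposite: the further the block falls behind, the smaller the p-value and the more firmly the rule says continue.

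The missing side also changes decisions. Read as a one-sided p-value for benefit, 0.774 means Z < -0.752. With 27 experimental and 26 control patients, that reading stops at 1 experimental vs 3 control (one-sided p = 0.86) and continues at 2 vs 2 (p = 0.52). The two-sided reading does the reverse (p = 0.28 and 0.97). Whoever runs the look would have to choose a reading, possibly with the data in hand.

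At stake is how many patients are enrolled, and have an extra bedside procedure, after a look that already points the wrong way. The validity of the final test is not at stake.

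**Working it through.** **Inputs.** From the documents: cut 0.774; look at 53 of 106 patients (information fraction 0.5); 53 per arm; rates 5% and 25%; two-sided alpha 0.05; 1:1 allocation. Assumptions: the 53 patients split 27 experimental and 26 control (the reverse split is given in brackets), and the chi-squared test is uncorrected unless stated. Counts are experimental vs control.

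**1. The cut on the Z scale.** Two-sided p > 0.774 means |Z| < 0.287, which is one-sided p = 0.387 at the upper edge.

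**2. The stated power.** Unpooled normal approximation:
- Drift = 0.20 / sqrt[(0.25×0.75 + 0.05×0.95)/53] = 3.004. The interim mean is 3.004 × sqrt(0.5) = 2.124, and the correlation of interim and final Z is sqrt(0.5) = 0.707.
- No look: 85.17%.
- Stop if |Z| < 0.287: 84.46%.
- Stop if Z < 0.287: 84.37%.
- Stop if Z < -0.752 (0.774 read as one-sided): 85.16%.

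The stated 84.5% fits the symmetric reading, though it barely separates that from the directional rule at the same cut.

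**3. What the rule does at particular results.** Conditional power (CP) is the chance of a significant final result favouring the block if the remaining patients follow 25% vs 5%.

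| Exp vs control | Two-sided p | Rule as written | CP |
|---|---|---|---|
| 1 vs 1 | 0.98 (0.98) | stop | 39% (43%) |
| 0 vs 1 | 0.30 (0.32) | continue | 26% (30%) |
| 1 vs 2 | 0.53 (0.57) | continue | 20% (23%) |
| 0 vs 3 | 0.069 (0.080) | continue | 3.0% (4.0%) |
| 1 vs 4 | 0.15 (0.17) | continue | 1.7% (2.4%) |
| 1 vs 6 | 0.037 (0.048) | continue | 0.15% (0.23%) |
| 0 vs 0 | undefined | no answer | 49% (53%) |

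With a continuity correction, the last three results with the block behind still continue: p = 0.22, 0.32 and 0.094 at 27 vs 26.

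**4. How often, by exact enumeration of all interim tables, both true rates 5%.**
- Rule as written stops: 19.8% (19.8%).
- Block behind, no stop: 35.6% (38.0%). This splits into one-patient deficits 20.3 (21.1) points, two-patient 10.3 (11.2), and three or more 5.1 (5.8).
- Of that total, tables with CP of about 3% or less: 5.1% (3.0%).
- 0 vs 0: 6.6%.
- Directional rule Z < 0.287 stops: 55.4% (57.8%) if 0 vs 0 continues, 62.0% (64.4%) if it stops.
- Expected N = 106 − 53 × P(stop): 95.5 (95.5) as written; 76.6 (75.4) directional; 73.1 (71.9) directional with a stop at 0 vs 0.
- With a continuity correction, the written rule stops 61% (61%) and the block is behind with no stop 15% (17%). The near-hopeless share is unchanged.

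**5. Other rates (a range, not document figures).** Tables with no stop and CP of 3% or less total 11.8% (11.8%) if both arms are at 10%, and 18.5% (19.1%) at 15%. If control is 15% and experimental 5%, the written rule stops 9% (8%) of the time and the directional rule 93% (94%).

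**6. Cost at the design rates, 25% vs 5%.** Stopping rises from 1.5% to 2.2% (1.8% to 2.7%). Exact power is 85.5% under both rules (85.4% vs 85.3%). With a continuity correction at both looks, exact power is about 77%.

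**The case against.** The best defence is that the symmetric region may be deliberate. If the match to 84.5% is trusted, it shows that such a region was designed, and an inner futility region is coherent with a two-sided test. If the match is not trusted, the reading is open, and a one-sided 0.774 would stop on many trailing results (24-26% at 5% vs 5%). The match does depend on the formula: with pooled variance the symmetric rule gives 81.5%, and by exact enumeration 85.5%. The documents do not say where 0.774 comes from. All of this stands as a limit on what was intended. It does not repair the text, because the direction is missing under either reading.

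Second, 36% overstates the harm. At 5% vs 5%, about 26 of the 36 points (27 of 38) have conditional power above 10%, where continuing is defensible, and much of the expected-N saving comes from stopping at one-patient deficits. That is right, and the near-hopeless share of 3-5% is the fairer measure of clear error. Even so, a rule that stops at 1 vs 1 has no reason to continue at 0 vs 1, where conditional power is lower.

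Third, the 10%, 15% and 15% vs 5% cases lie outside the documents, and nothing in the plan suggests that the block reduces opioid-free discharge. They are a range only. Higher rates in both arms are nevertheless plausible: the 5% is historical, and section 2.0 says usual care is already changing to an "enhanced surgical recovery bundle by using standardized non-narcotics and reducing initial IV-PCA settings".

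Fourth, the DSMB would see the direction and could act, and nothing obliges the trial to continue when p is at or below 0.774. That is true, but it leaves the plainest futility results to unscripted judgement. The expected-N figures also assume no accrual during the look, so the real saving would be smaller if enrolment is not paused.

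**Conclusion.** The concern holds. The rule is incomplete on one side; it is not reversed. Read with the only test the plan defines, it stops near-equality and has no stop once the block trails by more than |Z| = 0.287. It is also silent at 0 vs 0. If the block does nothing and both rates are 5%, 36-38% of looks find the block behind with no stop, of which 3-5 percentage points are near-hopeless; that share grows if both arms do better than 5%. The consequence is efficiency: about 19 to 20 more evaluable patients on average than a directional rule at the same cut with 0 vs 0 continuing (95.5 − 76.6 = 18.9; 95.5 − 75.4 = 20.1). Type I error, power and the final conclusion are essentially unchanged.

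This rests on a 27/26 split of the 53 patients, the uncorrected chi-squared test and no accrual during the look. A continuity correction shrinks the uncovered share to 15-17% but leaves the near-hopeless part as it was. It should be fixed because the gap is real and closing it costs almost nothing.

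**What to change.** Amend the interim paragraph in sections 4.0 and 5.0, one sentence in each, to settle three things:

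1. Name the interim test, including whether a continuity correction is used. This matters for the final test too, given the exact power of about 77% with the correction at both looks.
2. Make the rule directional at the same cut, analysed by allocated arm. For example: stop for futility if the experimental-minus-control Z is below 0.287, that is, if one-sided p for benefit exceeds 0.387. Equivalently, stop if two-sided p exceeds 0.774 or the estimate favours control.
3. State in advance what happens at 0 vs 0. About half the chance of success remains there at the design rates, so continuing is reasonable; stopping is the other option.

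If the symmetric region is intended, so that the trial can go on to show that the block is worse, say so.

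No extra patients or data are needed, and for the uncorrected test the stated 84.5% power can essentially stand. The one downside is that the trial would rarely run on to show formally that control is better, which is not its stated aim.

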5.0 Statistics and Justification of Sample Size

For the primary analysis, we will perform Chi-squared test to compare the proportion of patients who are opioid-free on the discharge date between the two arms. As a secondary analysis, we will also perform the Cochran–Mantel–Haenszel test to take into account the stratification factors. In addition, stratified logistic regression analysis will be carried out to assess the difference between the two arms after adjusting for the stratification factors and other patient characteristics at baseline. Similar analyses will be performed for other binary secondary outcomes, such as discharge Rx dosage/size total OME <200mg (yes vs. no), opioids usage on postoperative days 30, 90, 180, and 365 (yes vs. no), etc. Two sample t-test or Wilcoxon rank-sum test will be used to compare continuous secondary outcomes such as total inpatient OME, cost, QOL scores, pain prescription dosage at first discharge, etc. Other statistical analyses may be performed as appropriate.

Based on historical data, we anticipate that 5% patients in the control arm will be opioid-free in their discharge prescriptions, while with the additional TAP block in the experimental arm, it will increase the proportion to 25%. Under this assumption, the study will require 106 **patients (53 per arm)** in order to have 84.5% power to detect such a 20% difference, using two-sided Chi-squared test and with 5% significance level. East6.3 was used for the sample size calculation. Assuming a liberal 10% dropout rate, a total of 118 patients will be enrolled from our single institution. Based

on our historical operation volume of 120 patients per year, we anticipate the ability to complete enrollment within 1 year of opening the protocol. One interim analysis will be performed when half of the patients (N=53) have been randomized and received treatment. The trial will be stopped due to futility if the p-value is >0.774 .

- Power and significance: 84.5% power ($\beta=0.155$) and $\alpha=0.05$ (two-sided)
- Baseline estimate of control group with no opioids on discharge day: **5%**
- Estimate of experimental: **25%**
- Sample size per arm: 53 pts
- Assume 10% dropout: 59 per arm
 - [1 year to complete enrollment]

In order to enroll the total 118 patients, we will screen up to 140 patients in order to account for screen failures and those who are ineligible due to aborted surgeries.

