4.0 Research Plan and Methods

This is a **single-center phase II open-label randomized controlled trial** to assess the effect of an additional QL block on POD4 in patients undergoing pancreatic surgery with potentially curative intent. The primary endpoint is the proportion of patients who are **opioid-free on the discharge date**. Patients will be randomized with 1:1 ratio to receive either QL in OR + non-narc bundle +/- low-dose IV-PCA (control arm) or QL in OR and QL on POD4 AM + non-narc bundle +/- low-dose IV-PCA (experimental arm). The **allocation will be concealed until postoperative day 1** so that clinicians at the time of surgical consent will not be able to predict to which pathway the next enrollee will be assigned. Patients will be stratified based on pathway allocation (Green vs. Orange vs. Blue) and preoperative average daily OME use in the past 7 days (>5 mg vs. ≤ 5 mg OME).

Our **3 colored pathways are based on clinical predictors of pancreatic leak risk and thus median length of stay**. The median length of stay for Green (low-risk pancreaticoduodenectomy), Orange (high-risk pancreaticoduodenectomy), and Blue (distal pancreatectomy) patients is 6, 8, and 5 days, respectively. The length of stay affects the weaning, in that longer stays allow more time to wean off inpatient opioid use.

Method of Group Assignment and Randomization

Sequence Generation: Redcap will be used for 1:1 allocation with stratification for **postoperative pathway (Green, Orange, or Blue) which is determined preoperatively based on risk of pancreatic leak** and preoperative average daily OME use in the past 7 days (>5 mg vs. ≤ 5 mg OME).

Allocation Concealment and Mechanism: Allocation will be concealed at the time of enrollment from patients, providers, and researchers.

Implementation: Acute pain team, surgeons, advanced practice providers, fellows, and nurses will perform interventions and assessments per standard of care.

Blinding: All clinicians and patients will be **blinded from the allocation before surgery, intraoperatively, and until POD1**. The only difference in intervention will be the 2nd QL block which cannot be blinded.

Intervention Strategy:

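### Minor: randomisation is stratified by pathway and preoperative opioid use, but the primary chi-squared test ignores the strata; the already planned CMH test could be made primary at little cost

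*Combined protocol and SAP*

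**What the plan says.** Section 4.0 sets the randomisation strata: "Patients will be stratified based on pathway allocation (Green vs. Orange vs. Blue) and preoperative average daily OME use in the past 7 days", cut at 5 mg. Under Sequence Generation it repeats the same two factors: "Redcap will be used for 1:1 allocation with stratification for" pathway and preoperative OME. Three pathways by two OME levels make six cells. The same section gives a prognostic reason for pathway: "The length of stay affects the weaning, in that longer stays allow more time to wean off inpatient opioid use". It gives none for preoperative OME.

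Section 5.0 names the decisive test: "For the primary analysis, we will perform Chi-squared test to compare the proportion of patients who are opioid-free on the discharge date". The strata enter only afterwards: "As a secondary analysis, we will also perform the Cochran–Mantel–Haenszel test to take into account the stratification factors", followed by a stratified logistic regression. The sample size of 53 per arm rests on the unstratified test, "using two-sided Chi-squared test and with 5% significance level".

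The interim rule in section 4.0 is tied to the same endpoint: "The trial will be stopped due to futility if the p-value is >0.774 for the primary endpoint". The test behind that p-value is not named.

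The plan does not say whether the chi-squared or the CMH test is continuity-corrected, which strata the CMH test uses, or how sparse cells are handled.

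**The concern.** The plan balances the arms on two factors, and says one of them bears on the outcome, but leaves both out of the test that decides the trial. When randomisation is balanced within strata that predict the outcome, the arms differ less by chance than an unstratified test assumes. The test is then conservative: its type I error falls below 5% and some power is lost. A test on the randomisation factors recovers this without new data.

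The amount at stake depends on the control rate. The plan's 5% comes from a historical series, and section 2.0 says usual care is already being changed: "enhanced surgical recovery bundle by using standardized non-narcotics and reducing initial IV-PCA settings". No new rate is given. If the control rate is well above 5%, the outcome is more variable, and both the possible gain and the possible loss grow.

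**Working it through.** **Inputs from the documents.** Opioid-free rates 5% and 25%; two-sided alpha 0.05; 53 per arm (106); stated power 84.5%; 10% dropout, 118 enrolled; futility if p > 0.774 at N=53 (|Z| < 0.287); 1:1 allocation in six cells (section 5.0; strata and ratio from section 4.0).

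**The plan's own figure reproduces.**
- Unpooled standard error: sqrt[(0.05×0.95 + 0.25×0.75)/53] = sqrt(0.235/53) = 0.0666. Power = Φ(0.20/0.0666 − 1.96) = Φ(1.04) = 85.2%. Including the futility look gives 84.4-84.5%, which matches.
- Sample size per arm: (1.960 + 1.015)² × 0.235/0.20² = 52.004, rounded up to 53. Enrolment: 106/0.90 = 117.8, rounded up to 118.
- Pooled-variance formula: 83.2%. Exact binomial power of the chi-squared test at 53 per arm: 85.9% uncorrected, 78.1% corrected. The stated power therefore implies an uncorrected test.

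**Assumptions for the comparison.** The documents give no stratum shares, stratum outcome rates or block size. Assumed: pathways 40/30/30%, 20% of patients above 5 mg, permuted blocks of 4 within the six cells. Log-odds move by 0, 0.35 or 0.7 per pathway step, and by minus twice that for OME above 5 mg. The odds ratio (OR) between the extreme pathways, and for OME, is then 1, about 2 (e^0.7) or about 4 (e^1.4). Marginal rates are held fixed, with 200,000 simulated trials per main setting and no interim look.

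**Stratified test.** With a_k events among n_1k patients in one arm, m_k events in total, n_2k patients in the other arm and N_k patients in stratum k:

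CMH = [Σ(a_k − n_1k m_k/N_k)]² / Σ[n_1k n_2k m_k(N_k − m_k) / (N_k²(N_k − 1))], referred to chi-squared on 1 df, uncorrected.

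Four strata are used: each pathway at or below 5 mg, plus all patients above 5 mg. On the assumed shares about 21 of 106 patients are above 5 mg (0.20 × 106 = 21.2), or 6 to 8 per pathway over both arms. Only about 16 events are expected in the whole trial (53×0.05 + 53×0.25 = 15.9).

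**Power (%), chi-squared vs four-stratum CMH**

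| Strata effect | 5% vs 25% | Change | 20% vs 40% (assumed) | Change |
|---|---|---|---|---|
| None | 86.1 vs 85.9 | -0.2 | 62.8 vs 62.1 | -0.7 |
| OR 2 | 86.4 vs 86.6 | +0.2 | 62.8 vs 63.1 | +0.3 |
| OR 4 | 86.8 vs 88.0 | +1.2 | 63.2 vs 66.4 | +3.2 |

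**Type I error (%): none, OR 2, OR 4**
- Common 20% rate: chi-squared 5.1, 4.8, 4.3; CMH 4.8-4.9.
- Common 5% rate: chi-squared 4.7, 4.7, 4.5; CMH 4.6.

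**Sensitivity**
- Over 12 stratum mixes, from no effect to OR 4, the change is -0.3 to +1.3 points (5% vs 25%) and -0.9 to +3.7 (20% vs 40%).
- Only pathway prognostic, OR 4: 86.4 vs 86.9, and 62.9 vs 64.2.
- Constant 20-point risk difference in every stratum, 5% vs 25%: -0.1 to +0.1.
- Stronger effects (log-odds step of 1 between pathways, 2 for OME): about +1.8 at 5% vs 25%. The upper end of the range is therefore set by assumption.
- All six strata at 5% vs 25%: 85.8, 86.5, 87.9, nearly the same as four.
- No balance within strata (simple randomisation, the limiting case), 5% vs 25%: -1.3, -0.7, +0.6 with four strata; -2.1, -1.2, +0.4 with six. The lowest four-stratum power is 84.6%. At 20% vs 40%, four strata: -1.5, -0.5, +2.8.
- Continuity-corrected four-stratum CMH at 5% vs 25%: 77.8, 78.5, 80.3.
- The two tests reach different verdicts in 0.8-1.5% of trials at 5% vs 25%, and in 1.5-3.9% at 20% vs 40%.

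**Futility look at N=53.** Chance of p > 0.774: 1.8-1.9% (chi-squared) vs 1.8-2.0% (CMH) under 5% vs 25%, and about 27% for both under 5% vs 5%. Nothing is gained by moving the interim test.

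**The case against.** The strongest reply is that nothing is wrong. The chi-squared test is valid and at worst mildly conservative, and at present one test serves both sizing and final analysis and, on a natural reading, the futility rule. The stratified test and a stratified regression will be reported anyway, so the proposal only changes which result ranks first. At the planned rates the gain is smaller than the spread between ordinary power formulas (83.2% to 85.9%). It becomes visible only with stratum effects or a control rate that the documents do not give. At a common 5% rate the type I error argument nearly vanishes. Without balance within strata, the loss can be as large as the best gain at the planned rates. The four-way pooling is the reviewer's choice, not the plan's.

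All of this is true, and it limits the point to a minor one. It does not remove it. The plan itself specifies stratified allocation, which makes simple randomisation an extreme case; even there, four-stratum power at the planned rates stays at 84.6%, about the stated 84.5%. Analysing by the factors used to randomise needs no new data and uses a test the plan already contains. The silence on continuity correction and sparse strata remains whichever test is primary.

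**Conclusion.** The concern holds, as a minor improvement and not as a correction of an error. With allocation balanced within strata, an uncorrected four-stratum CMH test as primary changes power by -0.3 to +1.3 points at 5% vs 25%. At an assumed 20% vs 40% the change is -0.9 to +3.7 points. It also keeps the type I error near 5% where the chi-squared test falls to about 4.3% (common 20% rate, OR 4).

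These figures rest on assumed stratum shares, stratum effects up to OR 4 and blocks of 4. Stronger effects would give more; a constant risk difference would give almost nothing; lack of balance within strata with non-prognostic factors would cost about 1.3 to 1.5 points. The sample size need not change. The firmest part does not depend on which test is primary: a continuity correction would cost about 8 points, for the chi-squared test (85.9% to 78.1%) as for the CMH test.

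**What to change.** In section 5.0:

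1. Make the planned CMH test the primary analysis, two-sided at 5%, and state that no continuity correction is used.
2. Fix four strata in advance: each pathway at or below 5 mg OME, and one stratum for all patients above 5 mg.
3. Report the Mantel–Haenszel risk difference with its 95% confidence interval (with the Sato variance, coverage was 94.2-95.2% in the simulations).
4. Keep the uncorrected, unstratified chi-squared test as a sensitivity analysis.
5. State that the p > 0.774 futility look at N=53 uses the uncorrected, unstratified chi-squared test, and that the sample size is unchanged.

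If the chi-squared test stays primary, state that both it and the secondary CMH test are uncorrected, and name the CMH strata.

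The cost is a few sentences and no new data. The price is that the final test is no longer the one used for sizing. If the strata turn out not to be prognostic, up to about 0.3 point of power is lost at 5% vs 25% and about 0.9 point at 20% vs 40%. If allocation is also not balanced within strata, the loss is about 1.3 to 1.5 points.
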